5. SUBJECT ENROLLMENT

5.1 Recruitment and Pre-Screening

Breastfed infants with FPIAP, with either grossly visible bloody stool or microscopic bloody stools, excluding other causes, will be recruited at PNW or MGH Pediatric GI clinic. These individuals will be provided basic information about the study and ask potential participants to provide basic contact information and answer some study-specific questions as a pre-qualifier. Individuals who are interested to learn more will receive more details about the study, will be presented with an informed consent (IC), and will receive instructions as to how they are able to communicate with the study PI and other study team members to address any questions or concerns during the IC process and study duration.

5.2. Informed Consent Process

The parent of each infant participant will be required to sign an IRB-approved IC. Only participants for whom there is a signed and approved IC will be enrolled in the study. The IC will explain the study, and fully disclose its known risks and benefits by using simple, nontechnical terms wherever possible. The IC will include the elements required by the FDA in 21 CFR 50 and International Conference on Harmonization (ICH) guidelines. Parents will also be required to consent to the use of their protected health information (PHI) according to all applicable health information privacy regulations in the US. This authorization can be part of the IC or can be a separate document.

The investigator of the study is responsible for ensuring that a signed IC and authorization for use of PHI is collected from each participant that they enroll into the study at the time of that participant's enrollment. No study-related activities may be performed with, or by, any participant, and no data may be collected from any participant for study purposes prior to obtaining these consents and authorizations.

Participation in this study is voluntary and parents will be allowed to withdraw consent for their infant at any time for any reason with no impact on their eligibility to be treated for any adverse events or on their eligibility to receive other therapy.

5.3. Screening/Baseline

After signing the IC, parents will complete a screening questionnaire, demographics, medical history, and ConMeds to assess alignment with the eligibility criteria. Once eligibility at this point is confirmed, the study site will provide stool collection kits and the Study Product feeding kit. Parents will be provided with a binder, including logs and questionnaires that they will be expected to complete throughout the study.

Prior to start oral administration of *B. infantis* INF108F or placebo, the participant will have a physical exam with vital signs and parents will be expected to collect a baseline stool sample.

5.4. Randomization and Study Supply Shipment

Randomization lists will be maintained in a secured area by the study team. If the randomization key is shared such that blinding is compromised, the Principal Investigator will be notified.

Randomization will occur immediately after all screening and baseline tasks have been confirmed to be completed and baseline data has been deemed acceptable. Baseline tasks include:

- Confirming infant/mother eligibility
- Obtaining informed consent
- Confirming baseline data collection
- Confirming baseline stool specimen collection.

Only infants for whom acceptable baseline data and stool samples have been collected will be randomized into the supplementation phase of the study. Using the randomization key generated by an unblinded statistician and held by an unblinded study site team member, eligible infants will be assigned a randomization code and randomized to a study product arm. The unblinded team member will provide the enrolled patient's parents with

the appropriate Study Product Kit in accordance with the randomization key. Infants will be randomized in a 1:1 ratio to the following arms:

- 8.0×10^9 CFU *B. infantis* INF108F
- Lactose placebo

After randomization, the study team will provide the assigned feeding kit to the participant. Study supplies that will be provided include:

- Feeding kits to include 14 sachets of study product (*B. infantis* INF108F or lactose placebo depending on randomization), oral syringes, and mixing cups
- Stool collection kits

6. STUDY PROCEDURES

6.1 INVESTIGATIONAL PRODUCT(S)/INTERVENTION MATERIAL(S), OTHER STUDY PRODUCTS (CONTROLS/PLACEBOS)

6.1.1. Investigational Product(s) / Intervention(s)

INF108F

INF108F is formulated as water-soluble powder. The investigational study product is a probiotic, *B. infantis* INF108F. *B. longum* subsp. *infantis* INF108F (Infinant Health) was selected for this study due to its demonstrated ability to utilize many types of oligosaccharides found in breast milk (i.e., HMOs), including lacto-N-tetraose, lacto-N-neo-tetraose, 2'-fucosyllactose, 3'-fucosyllactose, 3'-sialyllactose, and 6'-sialyllactose.

The *B. infantis* INF108F was isolated from a healthy term breastfed infant. Its identity was confirmed by genetic sequencing of the organism by Infinant Health. Master stocks and working stocks were created and the strain is routinely tested for purity after fermentation. According to cGMP, the strain was re-isolated before creating the inoculum for the fermentation run.

The INF108F strain of *B. infantis* was produced by fermentation under cGMP conditions at a contract manufacturing organization (CMO). Following fermentation, the strain was centrifuged, freeze-dried, milled, and blended with lactose sourced from a Safe Quality Food (SQF) level 3 facility. The product was packaged by a second CMO into FDA compliant single-serving nitrogen-flushed polyester-faced laminated sachets with an oxygen and moisture barrier following cGMP. Each sachet contains approximately 600 mg of the blended powder containing at least 8×10^9 CFU *B. infantis* INF108F.

By way of its unique combination with human breast milk and utilization of HMOs, *B. infantis* INF108F is designated as a “Foods for Special Dietary Use” (FSDU). The term “special dietary uses”, as applied to food for man, is described in Chapter 1, Subchapter B, Part 105 of the Code of Federal Regulations, 21 CFR and defined in Part 105.3. It means foods supplying particular dietary needs which exist by reason of a physical, physiological,

pathological or other condition, such as conditions of diseases, convalescence, pregnancy, lactation, allergic hypersensitivity to food, underweight and overweight. Included in the definition are uses for supplying particular dietary needs which exist by reason of age, including but not limited to the ages of infancy (not more than 12 months old) and childhood (more than 12 months but less than 12 years).

Within the FDA, the Office of Food Additive Safety oversees a process for evaluating the safety of food ingredients that have a history of use, and can, by scientific consensus, be generally regarded as safe (GRAS). These food ingredients must complete a rigorous process of scientific and data review by independent qualified experts, who assess whether the product is safe under the conditions of its intended use. *B. infantis* INF108F gained GRAS status after successfully completing this process, with unanimous consensus by all independent qualified experts that this product is generally recognized as safe based upon the application of generally available and accepted scientific data, information, or methods (i.e., peer-reviewed scientific literature), and scientific principles for use in term infants.

GRAS status for *B. infantis* INF108F was obtained for a use level of up to 2.8×10^{10} colony forming units (CFU) per day. The current commercial serving size of *B. infantis* INF108F is 8.0×10^9 CFU/day.

INF108F Placebo:

INF108F Placebo is lactose[®] water soluble powder

The study product control is a lactose placebo. The lactose ingredient was sourced from a SQF level 3 facility and packaged into FDA compliant single-serving nitrogen-flushed polyester-faced laminated sachets with an oxygen and moisture barrier following cGMP. Each sachet contains 600 mg of lactose powder.

6.1.2 Study Product Handling, Storage and Compliance

Once a participant has been randomized, a feeding kit containing 14 sachets of *B. infantis* INF108F or placebo, oral syringes, and mixing cups will be provided. Parents will be instructed to store the supplement immediately upon receipt in their freezer until use.

Parents will be expected to record missed study product feedings in their daily feeding log. Compliance will be evaluated based on these data. Parents may also be requested at the end of the supplementation period to count the number of sachets remaining. Unused sachets may be kept by participants or disposed of.

6.1.3 Preparation and Administration

Parents will be trained on how to prepare and feed the study product to their infants. Infants enrolled into the control cohort will receive a lactose placebo and infants enrolled into the active cohort will receive *B. infantis* INF108F in lactose carrier. Both placebo and *B. infantis* INF108F feedings will be provided in powder form to be mixed in 3-5 mL (approximately 1 teaspoon) of breast milk each day for 14 consecutive days.

Study product cannot be initiated until 1) an infant has been deemed eligible for this study by the Investigator, 2) informed consent has been obtained, 3) the baseline stool sample has been collected and frozen by the parents, and 4) baseline study data has been obtained.

6.1.4 Accountability of Investigational Product(s) / Intervention(s)

Under Title 21 of the Code of Federal Regulations (21CFR §312.62) the investigator will maintain adequate records of the disposition of the investigational product(s) / intervention material(s), including the date and quantity of the product received, to whom the product was dispensed (participant-by-participant accounting), and a detailed accounting of any investigational product(s) / intervention material(s) accidentally or deliberately destroyed.

Records for receipt, storage, use, and disposition will be maintained by the study site. A Master Dispensation Log will be kept current. This log will contain the identification of each participant and the date and quantity of investigational product(s) / intervention material(s) dispensed. Any product that remains unused at the end of study will be destroyed.

All records regarding the disposition of the investigational product(s) / intervention material(s) will be available for inspection by the Clinical Research Associate (CRA).

6.1.5 Assessment of Compliance with Investigational Product(s) / Intervention Material(s)

Every study subject will be asked to record consumption of their feedings of INF108F/placebo in a daily feeding log. Investigational product compliance will be recorded as a percentage, calculated as the number of days of reported consumption divided by the number of days of supplementation expected.

For participants who are withdrawn prior to the end of the supplementation period, percent adherence will be based on the number of days active in the study prior to withdrawal.

6.1.6 Modification or Discontinuation of Investigational Product(s) / Intervention Material(s)

The parents may withdraw their infant from the study at any time by notifying the study team. Participants may be withdrawn from the study by the investigator if study procedures have not been followed or if the investigator determines the participant is not able to safely continue with the study due to an adverse event or other health-related issue. If greater or equal to 20 percent drop-out occurs, infants may be replaced to assure adequate statistical power.

6.2. OTHER MEDICATIONS

6.2.1 Concomitant Medications

Concomitant medications may be used as necessary throughout the study unless noted in section 6.2.

6.2.2 Prohibited Medications and Dietary Ingredients

Medications and dietary ingredients prohibited during the study include:

For Infant:

- Any probiotics (including infant formulas containing probiotics)
- Antibiotics (oral or systemic)
- Infant formula greater than half of the infant's daily nutrition intake
- Solid food

For Mother:

- Antibiotics
- Probiotics containing *B. infantis*

6.3. STUDY ASSESSMENTS AND PROCEDURES

6.3.1 Efficacy Assessments

6.3.1.1 Primary objective

The primary objective of the study is to assess changes to the gut microbiome composition (including *B. infantis* colonization) in infants with FPIAP over a 4-week period (*B. infantis* INF108F vs placebo)

6.3.1.2 Secondary Objectives

The secondary objectives of this study are to evaluate: clinical symptoms including blood in stool, stool frequency, GER, feeding difficulties, sleep disturbance and poor growth

6.3.1.2.1 Blood in stool Blood in stool will be assessed by daily hemoccult stool test on Days 0, 1-14, 21 (+/- 1 day), 28 (+/- 1 day)

6.3.1.2.2 Stooling Infant stooling will be assessed by daily log capturing frequency, consistency, night stooling, and presence of mucus or gross blood

6.3.1.2.3 Infant GER Infant GER will be assessed by standard Reflux Questionnaire on Day 7, 14, 21, and 28

6.3.1.2.4 Infant Sleep Infant sleep duration/quality will be assessed by Questionnaire on Day 7, 14, 21, and 28

6.3.1.2.5 Infant Feeding Infant feeding difficulties will be assessed by Questionnaire on Day 7, 14, 21, and 28

6.3.1.2.6 Infant Growth Infant growth will be monitored at weekly visits by measuring weight, length, and head circumference

6.3.1.2.7 Adverse Events Supplement-related adverse events will be recorded by parents in a health log, in consultation with the study team and PI.

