1.4 Rationale for Selection of Investigational Product(s) / Intervention(s) and Regimen

B. infantis INF108F has been used in other trials and has been shown to be safe and well-tolerated in infants (term and preterm) when supplemented daily for variable durations. Studies of this strain in breastfed infants

demonstrate a significant change to the gut microbiome composition within days of initiating the supplement. This change generally persists beyond the supplementation period if infants continue to receive breast milk as all or part of their diet.

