9.2.3 Efficacy Analysis

Primary Endpoint(s) The primary objective of the study is to assess the effectiveness of the probiotic, *B. infantis* INF108F, on modulating the gut microbiome composition of breastfed infants diagnosed with FPIAP from Baseline to Day 28, including colonization of INF108F. This will be measured using stool 16S analysis and quantitative PCR. Treatments will be compared using a Wilcoxon Rank Sum test.

Secondary Endpoint(s) The secondary objectives of this study as measured:

- Evaluating the reduction in stool frequency and improvement of stool consistency by Day 7 using Questionnaire
- Evaluating the improvement of infant GER symptoms by Day 14 using Questionnaire. Reduction by 50 percent from Baseline to Day 14 Infants with a reduction in the number of crying/fussing episodes of greater than or equal to 50 percent on Day 14 will be counted as a success. The number of successes per treatment group will be compared using a Chi-square or Fisher's Exact test, as appropriate.
- Evaluating the improvement of feeding difficulties by Day 14, using Questionnaire. The number of successes per treatment group will be compared using a Chi-square or Fisher's Exact test, as appropriate.

- Evaluating the improvement of infant's sleep by Day 14, using Questionnaire.
- Changes of stool cytokine profile by Day 28. The changes from baseline to Day 28 will be compared for the two groups using a repeated measures ANOVA.

Safety Analysis Fisher's Exact Test will also be used to compare treatment groups for SAEs and AEs resulting in withholding or discontinuing the study products. Adverse events will be summarized. Frequencies and percentages of subjects with treatment-emergent adverse events (TEAEs), serious TEAEs and TEAEs causing premature discontinuation will be provided by treatment group. An AE is treatment emergent if it 1) occurs after the first dose of randomized study treatment or 2) if it is present prior to receipt of randomized study treatment but worsens in severity or increases in frequency after the first dose of randomized study treatment.

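### Section 9.2.3 names only Day 14 for reflux, feeding and sleep; one baseline-adjusted mixed model on the scheduled questionnaires would use the data better and give a named Day 28 comparison

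*Combined protocol and SAP*

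**What the plan says.** **Collection.** Section 6.3.1.2 sets the same four days for three instruments: reflux ("Infant GER will be assessed by standard Reflux Questionnaire on Day 7, 14, 21, and 28"), sleep ("Infant sleep duration/quality will be assessed by Questionnaire on Day 7, 14, 21, and 28") and feeding ("Infant feeding difficulties will be assessed by Questionnaire on Day 7, 14, 21, and 28"). It lists no Day 0 questionnaire. Table 1 does tick Questionnaire on Day 0 and on every later column up to Days 15-27, but not on Day 28. It also ticks a clinician symptom tool on Days 0, 7, 14 and 28.

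**Named analysis.** Section 9.2.3 covers each symptom in one bullet:
- Reflux: "Evaluating the improvement of infant GER symptoms by Day 14 using Questionnaire". Success is then defined by "Infants with a reduction in the number of crying/fussing episodes of greater than or equal to 50 percent on Day 14", with a chi-square or Fisher's exact test.
- Feeding: "Evaluating the improvement of feeding difficulties by Day 14, using Questionnaire". Successes are compared in the same way, but success is not defined.
- Sleep: "Evaluating the improvement of infant's sleep by Day 14, using Questionnaire". No test is named.

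**General rules.** Section 9.2.2 says that all CRF data will be analysed and that summaries will be given by time point where relevant. For continuous data it allows one-way ANOVA at individual time points or repeated measures ANOVA over all of them, without choosing. Categorical data get Fisher's exact or chi-square tests. Missing data are not imputed.

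**Endpoint list.** Section 3.1.2 gives reflux, feeding and sleep no time point. It sets Days 7, 14 and 28 for occult blood, visible blood and stool frequency. The primary analysis in 9.2.3 runs from baseline to Day 28.

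**The concern.** Parents complete reports after Day 14 that no named analysis takes up. Whether Days 21 and 28 enter a comparison, and by which method, would be settled only by the generic wording of 9.2.2, possibly after results are known. Section 1.4 says of the microbiome change: "This change generally persists beyond the supplementation period if infants continue to receive breast milk". A Day 28 look at these symptoms beside the Day 28 microbiome result is therefore of interest, and it is not named.

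The method matters as well. A success count discards information that a score would keep. It also uses only infants with the Day 14 report, in a trial that expects 20% to drop out and does not impute. At about 20 completers per arm there is little information to spare.

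**Working it through.** **Plan's own figures.** Section 9.1.1: 100 screened × 0.5 = 50 randomized; 50 × 0.8 = 40 completers. In reverse, 40 / (1 − 0.20) = 50. With 1:1 allocation that is 20 per arm, as the synopsis says. The headcounts reproduce. The plan states no alpha, power, effect size, SD or correlation, so everything below is illustrative.

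**Assumptions.** Each questionnaire yields a roughly continuous score; equal variance (set to 1) at each report; equal correlation ρ between any two reports, 0.4 to 0.8; complete data; 20 per arm; two-sided 0.05.

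**1. Do Days 21 and 28 sharpen the Day 14 contrast?** With a separate mean per day and complete data, the relative variance at one visit is 1.00 whether 1, 2 or 4 visits are modelled (checked at ρ = 0.5 and 0.7). They do not. Under dropout, a mixed model lets an infant who leaves after Day 7 still inform Day 14, and one who leaves after Day 14 still inform Day 28. Up to 50 − 40 = 10 infants are concerned; the plan does not say when they would leave.

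**2. Baseline adjustment at Day 14.** Variance goes from 1 to 1 − ρ².
- ρ = 0.4: √0.84 = 0.92, a cut of 8%
- ρ = 0.5: √0.75 = 0.87, a cut of 13%
- ρ = 0.8: √0.36 = 0.60, a cut of 40%

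Against a simple change score, whose variance is 2(1 − ρ), the variance ratio is (1 + ρ)/2, or 0.70 to 0.90. The standard error falls by 16% to 5%.

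Power at an assumed Day 14 difference of 0.7 SD and ρ = 0.5 is 58% unadjusted and 70% adjusted.

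**3. Dichotomising.** Suppose success splits the same score at its overall median. At 0.7 SD the success rates are Φ(0.35) = 0.64 and 0.36. Power with 20 per arm is about 28% (Fisher) or 39% (chi-square), against 58% for the score itself. The plan's reflux rule is a 50% reduction in episodes, not a median split, so this shows direction and rough size only.

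**4. Four-day average.** Variance is (1 + 3ρ)/4, against 1 for one report. With baseline it is (1 + 3ρ)/4 − ρ², against 1 − ρ².

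| ρ | SE ratio, no baseline | SE ratio, with baseline |
|---|---|---|
| 0.4 | √0.55 = 0.74 | √(0.39/0.84) = 0.68 |
| 0.5 | √0.625 = 0.79 | √(0.375/0.75) = 0.71 |
| 0.8 | √0.85 = 0.92 | √(0.21/0.36) = 0.76 |

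The cut is 8 to 26%, or 24 to 32% with baseline.

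**5. When does the average help power?** The SE ratio is also the break-even. The average effect must be at least 74 to 92% of the Day 14 effect, or 68 to 76% with baseline. Two patterns:
- Full effect on Days 7 and 14, fraction f on Days 21 and 28, ρ = 0.5: (2 + 2f)/4 ≥ 0.791 gives f ≥ 0.58; with baseline, ≥ 0.707 gives f ≥ 0.41.
- Effects of 50, 100, 75 and 50% of the Day 14 effect average 69%. Without baseline the average loses at every ρ in the range; with baseline it is close to break-even at ρ = 0.4 and loses at higher ρ.

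**The case against.** The strongest reply is that the plan already covers the later days. Section 9.2.2 commits to analysing all CRF data and offers a repeated measures ANOVA over all time points. A reader might infer from 9.2.3 that Days 21 and 28 are unused; the documents do not support that. What remains is that 9.2.2 names no time point, contrast or priority for these questionnaires and does not choose between its two ANOVAs. It also applies the repeated-measures rule to continuous data, whereas 9.2.3 turns reflux and feeding into success counts. For a sleep score, 9.2.2 could apply as it stands.

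A reader might also infer that symptoms are never compared at the primary time point. That is wrong: occult blood, visible blood and stool frequency have Day 28 endpoints in 3.1.2. The gap concerns reflux, feeding and sleep only.

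Thirdly, Day 14 is the end of supplementation and a coherent time point. Choosing it does not in itself lose precision, as step 1 shows. The gain in step 4 belongs to a different estimand, in which two of the four reports fall after product stops. That objection stands in full, and it is why the four-day average should not replace Day 14 as the main comparison.

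Finally, the model needs numeric scores and a Day 0 report. The documents do not describe the scoring, and 6.3.1.2 and Table 1 disagree about Day 0. That is a condition on the fix, not a reason against it.

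**Conclusion.** The point holds as a modest, low-cost improvement. Section 9.2.3 names only Day 14 for these three symptoms, its method for reflux and feeding discards information, and sleep has no named test. None of the three has a named Day 28 comparison.

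The benefit of a mixed model comes from three sources: baseline adjustment (8 to 40% off the Day 14 standard error against an unadjusted score, 5 to 16% against a change score), analysing the score rather than a success count, and keeping earlier reports from infants who leave. The first two sizes rest on assumed correlation and scoring; the third depends on dropout timing that the plan does not give.

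The 8 to 26% (24 to 32% with baseline) reduction from using four reports should not be read as precision that the plan loses. It applies to the four-day average alone, and becomes power only if the effect holds up after Day 14.

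**What to change.** In 9.2.3:
- Analyse each reflux, feeding and sleep score in one mixed model on Days 7, 14, 21 and 28, with arm, day and arm-by-day, and the Day 0 score as covariate.
- Keep the Day 14 arm difference as the named contrast for each symptom.
- Report the Day 28 difference and the four-day average, each with a 95% interval, as supportive.
- Keep the 50 percent reflux responder comparison as a supportive analysis.

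Reconcile 6.3.1.2 with Table 1: the former lists a Day 28 questionnaire and no Day 0 one; the latter ticks Day 0 and not Day 28. The covariate needs the first and the Day 28 contrast needs the second.

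Cost: SAP wording and slightly more analysis. If the responder rule counts as a principal feature of the analysis plan, section 9.4 requires a protocol amendment subject to IRB review. No new data are needed provided the Day 0 and Day 28 questionnaires are in fact collected. The change should be made before unblinding.

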3.1.2. Secondary Endpoints

- The percentage of patients testing negative for blood in stool by Study Day 7, 14 and 28 by hemoccult testing
- The percentage of patients with no gross/visible blood in stool by Study Day 7, 14 and 28 by parental report
- Changes to stool frequency by Study Day 7, 14 and 28
- Changes to clinical symptoms including GER, feeding difficulties, sleep disturbance and poor growth
- The occurrence of supplement-related adverse events

3.1.3 Biomarkers / Exploratory Endpoints:

- Fecal calprotectin levels
- Fecal pH levels
- Fecal metabolomics
- Markers of inflammation and enteric cytokines including, but not limited to, IL-1, IL-8 and TNF-alpha in stool
- Levels of eosinophil-related granular proteins in stool
- Intestinal permeability/integrity markers including, but not limited to, lipocalin (NGAL)

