4. SUBJECT SELECTION

4.1 Inclusion Criteria

Individuals who meet all of the following criteria are eligible for enrollment as study participants. Potential candidates will be identified at the Pediatrics at Newton Wellesley (PNW) and MGH Pediatric Gastroenterology Clinic. The recruitment will occur at Newton Wellesley Hospital or Massachusetts General Hospital.

- Infants, male or female, of all ethnic/racial groups, with a gestational period of 37 to 42 weeks
- Infants aged 1-90 days old with a documented FPIAP with either gross blood or microscopic blood in stools, without other possible causes
- Infants must be exclusively breastfed or at least half of oral intake is from breast feeding or from expressed breast milk
- A willing parent or legal guardian will sign the consent form either electronically or with a wet ink signature

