6.6.4 Physical Examination

This will include measurement of vital signs, including weight, temperature, heart rate, and blood pressure, and physical examination including the skin, ears, nose and throat, abdomen, lungs, and heart.

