9.2.2 Study Participant Populations

Randomization Approximately fifty (50) infants will be randomized in a 1:1 ratio to treatment probiotic or placebo. Randomization will occur immediately after all baseline period tasks have been confirmed to be completed and provide acceptable data.

Populations for Analyses The modified Intent to Treat (mITT) population will include all infants who are randomized and receive at least one supplementation. The Per Protocol (PP) population will include all randomized participants who do not have major protocol deviations. Major protocol deviations will be defined prior to unblinding of the data. Analysis on primary and secondary objectives will be completed based on the mITT population and the PP population; analysis on the exploratory objectives (perception of treatment) will be completed based on the mITT population.

Descriptive Statistics Descriptive statistics (mean, median, and standard deviation, minimum and maximum) of the quantitative variables will be summarized using number of subjects (n). The qualitative variables will be summarized using counts and percentages. All summaries will be presented by treatment group and time point (where relevant).

All CRF and laboratory data will be analyzed. Comparisons between treatment groups will be performed using Fisher's exact test or Pearson's Chi-Square test for categorical data and one-way ANOVA with Tukey's post hoc comparisons for individual timepoints or two-way repeated measures ANOVA for all timepoints for continuous data. Mean and standard deviations for certain groups and timepoints will be used as estimates in power calculations for future studies. Missing data will not be imputed in this study.

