9.2.4 Study Participant Baseline Characteristics and Demographics

Summary of descriptive statistics for baseline and demographic characteristics will be provided for all enrolled participants. Demographic data will include age, race, sex, body weight, and height; these data will be presented in summary tables.

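### Poor growth is a secondary endpoint without its own analysis, and the default ANOVA ignores age and sex in infants who enter at 1–90 days

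*Combined protocol and SAP*

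**What the plan says.** Growth is a secondary endpoint. Section 3.1.2 (and the synopsis) lists "Changes to clinical symptoms including GER, feeding difficulties, sleep disturbance and poor growth", and section 6.3.1.2 repeats poor growth among the secondary objectives. Section 6.3.1.2.6 says how it is observed: "Infant growth will be monitored at weekly visits by measuring weight, length, and head circumference". Entry is open to "Infants aged 1-90 days old with a documented FPIAP" (section 4.1).

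Section 9.2.3 sets out analyses for stooling, GER, feeding, sleep and stool cytokines, but none for growth. What remains is the general rule in section 9.2.2. It says "All CRF and laboratory data will be analyzed", and it compares arms by one-way ANOVA at individual timepoints or by "two-way repeated measures ANOVA for all timepoints for continuous data". No age, sex or baseline covariate is named. The documents mention no z-score, percentile or growth reference, and they do not define poor growth.

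The data needed to standardise are already planned. Section 9.2.4 says: "Demographic data will include age, race, sex, body weight, and height".

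Two other places do not match section 6.3.1.2.6. Table 1 shows study visits and physical examinations on Days 0, 7, 14 and 28, and none on Day 21. Section 6.6.4 describes the examination thus: "This will include measurement of vital signs, including weight, temperature, heart rate, and blood pressure". Length and head circumference are not named there.

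**The concern.** Whether growth is poor can only be judged relative to age and sex. The same weight may be unremarkable in a two-week-old and low in a three-month-old. A default analysis of kilograms and centimetres therefore does not address the listed endpoint, however precise it is.

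Precision suffers too. With entry ages up to 89 days apart and about 20 completers per arm, part of the spread between infants is simply age. That widens the interval for the arm difference, and a chance difference in mean age between arms would appear as a growth difference in either direction. At stake is the readability of one secondary endpoint.

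**Working it through.** **The plan's own figures.** Section 9.1.1: 100 × (1 − 0.5) = 50 randomised, and 50 × (1 − 0.2) = 40 completers, or 20 per arm at 1:1. These reproduce. The plan gives no alpha, power, effect size or SD for growth.

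**Assumptions, not from the documents.** Two-sided 5% alpha, 80% power, normal approximation, and entry ages uniform over 1–90 days. For weight at one timepoint: gain of 20–40 g/day and SD at fixed age of 0.4–0.6 kg. For 28-day change: mean gain falls by 0.2–0.6 kg per 28 days across the age range, and SD of gain at fixed age is 0.15–0.30 kg.

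**Step 1: common factors.** SD of age = 89/√12 = 25.7 days. Detectable difference at 20 per arm = (1.960 + 0.842) × √(2/20) = 0.886 SD.

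**Step 2: raw weight at one timepoint.** Total SD = √(SD at fixed age² + (daily gain × 25.7)²).
- Smallest age effect: 20 g/day, SD 0.6 kg. √(0.36 + 0.264) = 0.79 kg; age is 42% of the variance; SD ratio 0.79/0.6 = 1.32.
- Largest: 40 g/day, SD 0.4 kg. √(0.16 + 1.056) = 1.10 kg; age is 87%; SD ratio 2.76.
- Over the whole grid, the detectable difference is 0.58–1.05 kg raw, against 0.35–0.53 kg with age removed.

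**Step 3: 28-day change.** SD due to age = fall in gain/√12, from 0.2/√12 = 0.058 kg to 0.6/√12 = 0.173 kg.
- Smallest: fall 0.2 kg, SD 0.30 kg. √(0.09 + 0.0033) = 0.306 kg; age is 4%; SD ratio 1.02.
- Largest: fall 0.6 kg, SD 0.15 kg. √(0.0225 + 0.030) = 0.229 kg; age is 57%; SD ratio 1.53.
- Over the grid, the detectable difference is 0.14–0.31 kg, against 0.13–0.27 kg with age removed.

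**Step 4: the same noise seen as chance imbalance.** The SD of the difference in mean age between arms is 25.7 × √(2/20) = 8.1 days. In raw weight that is 8.1 × 0.020 = 0.16 kg to 8.1 × 0.040 = 0.32 kg. In 28-day change it is 8.1 × 0.2/89 = 0.02 kg to 8.1 × 0.6/89 = 0.05 kg.

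**Step 5: sensitivity to the age spread.** Section 1.1 places FPIAP onset at 2 weeks to 2 months. If entry ages were uniform over days 14–60, the SD of age is 46/√12 = 13.3 days. The SD ratio falls to 1.09–1.66 for raw weight and 1.00–1.16 for change.

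**The case against.** A reader might infer that the plan intends to compare raw weight, length and head circumference. The documents do not say so. Section 6.3.1.2.6 is a measurement plan, and z-scores are computed from exactly these measurements, so nothing in the text rules them out. What stands is narrower: growth has no analysis of its own, and the rule that would govern it by default adjusts for neither age nor sex.

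A reader might also infer that age swamps any effect. That fits, at most, a single-timepoint comparison of raw values. Section 9.2.2 equally allows repeated measures ANOVA, whose group-by-time test works within infants, and section 3.1.2 words the endpoint as a change. On change, age matters modestly (step 3), and less still if entry ages cluster near disease onset (step 5).

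Nor is this bias. Section 9.2.2 states: "Approximately fifty (50) infants will be randomized in a 1:1 ratio to treatment probiotic or placebo". Randomisation makes age a source of noise and chance imbalance, not of systematic error.

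Finally, poor growth is hard to read partly because it is undefined. Table 1 includes a clinician symptom tool, and the documents do not say whether it covers growth. Growth is also absent from the objectives in section 2.2. These points lower the weight of the matter. They do not supply the missing metric or analysis.

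**Conclusion.** The point holds as a free improvement of low severity. Growth falls to a default analysis that is less precise than it need be and that, on raw values, cannot express growth that is poor for age and sex. Under the assumed inputs, the loss is substantial for raw weight at one timepoint (SD ratio 1.3–2.8) and modest for change (about 1.02–1.5). These figures cover weight only; nothing was computed for length or head circumference. They also assume that standardising removes the whole age component. The case for a standardised metric does not depend on them, because it follows from what the endpoint is meant to describe. The primary conclusion is not affected.

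**What to change.** In section 9.2.3, add a growth analysis:
- Convert weight, length and head circumference to age- and sex-specific z-scores from a named infant growth reference, using age on the day of measurement.
- Compare Day 28 z-score between arms by ANCOVA with the Day 0 z-score as covariate. Using change from Day 0 as the response in the same model gives the same treatment estimate.
- Report raw values descriptively.
- If poor growth is to be counted as a yes/no outcome, define it on the z-score scale before unblinding.

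Reconcile the weekly visits of section 6.3.1.2.6 with Table 1, which has no Day 21 visit, and with section 6.6.4, which names weight but not length or head circumference.

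The cost is wording. Age and sex are already collected, and Day 0 and Day 28 examinations are already scheduled. No infants or visits are added for this analysis, and no measurements beyond those section 6.3.1.2.6 already calls for.
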